Appendix B

INSULIN, SUBCUTANEOUS ORDERS-SUPPLEMENTAL ORDERS ADULT, NON-PREGNANT PATIENTS

PATIENT NAME

DATE OF BIFTH (DOB)

MEDICAL RECORD NUMBER(MRN)

ACCT. NO/CSN

Orders preceded with a box must be checked to activate. All other orders are effective unless modified. Complete blanks to specify information not predefined. Initial each modification made to the order set, e.g., additions, deletions, strikeouts. Initial each internal page in bottom right corner. Statements in italics represent decision support for providers completing the order set; these statements are not part of the physician order(s). Provide corporate identification, sign, date and time last page.

Must be on Continuous Glucose Monitor Research Protocol and must be implemented in coordination with Diabetes APRN.

- Maintain current subcutaneous insulin order set and insure that it includes an HS correction option.
- 2. Implement the below orders in addition to currently active insulin order set.
- Obtain additional finger stick blood glucose as indicated per research protocol and/or directed by diabetes research team or designee.
- For any finger stick blood glucose between 70-79 mg/dL, give 1 tube (15 gm) glucose gel PO STAT or for patients unable to take PO, give D50W 25mL IVP STAT; recheck blood glucose 15 minutes after administration of glucose gel or D50W.
- If at any point after HS and before 4 am fingerstick blood glucose is greater than or equal to 200 mg/dL and no correction dose given in last three hours, administer correction dose per selected scale below.

Correction Coverage: Insulin Lispro (Humalog) subcutaneously per selected scale and blood glucose value:

Blood Glucose (Default Scale)	Insulin Scale				
	☐ Very Low	Low	□ Moderate	□High	
201-250 mg/dL	1 unit	2 units	3 units	4 units	
251-300 mg/dL	2 units	3 units	5 units	6 units	
301-350 mg/dL	2 units	4 units	6 units	8 units	
351-400 mg/dL	3 units	5 units	8 units	10 units	
Greater than 400 mg/dL	3 units	6 units	9 units	12 units	

6. Above orders to be discontinued when patient is discontinued from CGM research study.

Г	Prescriber Signature	Printed Name or Corporate ID				Date and Time
\vdash	Transcriber Signature	Printed Name or Corporate ID	Date and Time	RN Signature	Printed Name or Corporate ID	Date and Time
L						

PO 100-N\$8720-399\$W

S-INSCGM 100-NS8720-399SW (8/22/18)

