 - III. Point-of-care blood glucose tests (POC) > 200 mg/dL or chemistry glucose >200 mg/dl on at least three different time points within the last 24 hours, before consenting.
 - c. English or Spanish speaker.

Exclusion Criteria:

- 1. Pregnant
- 2. Patient in ICU and with insulin drip (participants in ICU not on the insulin drip are allowed)
- 3. Known allergy to adhesives
- 4. Anticipated CT/MRI/diathermy procedure within 24 hours from admission (patients with a planned operation within 24 hours from admission may be included in the study before the operation see Sensor Insertion/Transmitter Connection section of the protocol).
- 5. Current participation in any medication or device research study
- 6. Have any condition that in the opinion of the Principal Investigator is deemed contraindicated for study participation

Overview:

All patients with type 1 or type 2 diabetes who meet study criteria will be invited to participate in the study. All patients included in the study will be followed by an advanced practice diabetes nurse (APN) for glucose management during their hospitalization. All patients included in the study will receive a CGM. Patients with type 2 diabetes will be randomized to control (blinded CGM glucose values) or intervention (CGM blood glucose values will be used to aid with glucose management during the hospitalization). In addition, a research only supplemental order set will be implemented for all study participants. The order set focuses on any glucose point of care test that is between 70-79 mg/dL at any time or ≥ 201 mg/dl at night, between 9pm and 4am (21:00-04:00). (Appendix B). The goal is to prevent hypoglycemia and hyperglycemia for all study patients. The advanced practice diabetes nurse will work with the physician in charge of the patient's care as well as the patient's care team.

Patients with type 1 diabetes:

Patients with type 1 diabetes will receive a CGM. The CGM device will be placed for the length of the patient's stay with sensor changes at 240 hours (10 days) post insertion or as needed. Calibrations are not required for the IUO CGM and will not be performed routinely.

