The CGM device will be kept unblinded, which means that the data can be viewed at the patient's Monitoring devices will be set to alarm if rate of change is trending towards hypoglycemia with a value of ≤ 90 mg/dL or trending towards severe hyperglycemia with a value of \geq 250 mg/dL. Wireless communication will allow for assigned personnel to view CGM values at real time and also be alerted by alarms set by specifications above. Nursing staff assigned to the patient will then conduct POC testing. If the initial POC testing value after alarm is 70-79 mg/dL then the patient will receive 15 gm glucose gel with follow up POC testing per APN recommendations, based on supplemental order set (PFO). Below 70mg/dl, patients are treated based on established hypoglycemia standing orders. If the initial POC testing value after alarm is ≥ 201 mg/dL then insulin adjustments will be individualized based on the patient's clinical scenario. Patients receive supplemental insulin for hyperglycemia only if POC testing ≥ 201mg/dl is between 9pm and 4am (21:00-04:00) and they have not received any additional insulin for the Thereafter, follow up POC testing will continue according to APN past three hours. recommendations. In addition, insulin adjustment algorithms will be used by the APN after CGM and POCT values ongoing daily review and communication with the physician and care team, to maintain glucose levels within goal. Communication between glucose management team, nursing staff and monitoring physician may take place more often if trends towards hypoglycemia or hyperglycemia are visible.

CGM data will automatically be uploaded to a commercially available, web-based service (Dexcom ClarityTM Diabetes Management Software) using the Scripps' wifi connection. This system enables research staff to review historical CGM data and also provides summary reports, including average glucose and patterns of high and low glucose.

POC glucose values, HbA1c level at admission and usual care laboratory glucose values will be collected as well. A follow-up questionnaire will take place within 7 days from discharge (including discharge date) to assess any adverse events and to obtain patient satisfaction data regarding his/her hospital stay and use of the CGM device.

For data analysis, the percentage of patient-days with average glucose within 70-180 mg/dL will be compared to historical baseline data.

Patients with type 2 diabetes:

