All type 2 patients enrolled will receive the CGM device, but patients will be randomized to control (CGM glucose values are blinded to APN, care team and researchers) or intervention (CGM blood glucose values will be used to aid with glucose management during the hospitalization). CGM data will be compared between both groups during data analysis. CGM data will be blinded for all type 2 patients. This means that data will not be viewed at the patient's bedside, but will be reviewed remotely by research staff for the intervention group. In short, the CGM device will be placed for the length of the patient's stay with sensor changes at 240 hours (10 days) post insertion or as needed. Calibrations are not required for the IUO CGM and will not be performed routinely.

For the intervention group, monitoring devices will be set to alarm remotely if rate of change is trending towards hypoglycemia with a value of ≤ 90 mg/dL or trending towards severe hyperglycemia with a value of > 250 mg/dL. Wireless communication will allow for assigned personnel to view CGM values at real time and also be alerted by alarms set by specifications above. Nursing staff assigned to the patient will then conduct POC testing. If the initial POC testing value after alarm is 70-79 mg/dL then the patient will receive 15 gm glucose gel with follow up POC testing per APN recommendations, based on supplemental order set (PFO). Below 70mg/dl, patients are treated based on established hypoglycemia standing orders. If the initial POC testing value after alarm is ≥ 201 mg/dL then insulin is administered in accordance with supplemental research order set. Patients receive supplemental insulin for hyperglycemia only if POC testing ≥ 201 mg/dl is between 9pm and 4am (21:00-04:00) and they have not received any additional insulin for the past three hours. In addition, APNs will recommend insulin adjustments based on daily review of CGM trends and POCT values. Communication between glucose management team, nursing staff and monitoring physician may take place more often if trends towards hypoglycemia or hyperglycemia are visible.

CGM data will automatically be uploaded to a commercially available, web-based service (Dexcom ClarityTM Diabetes Management Software) using the Scripps' wifi connection. This system enables research staff to review historical CGM data and also provides summary reports, including average glucose and patterns of high and low glucose.

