We hypothesize that instituting the broad use of subcutaneous CGM with wireless transmission to an advanced practice diabetes team for high risk patients with type 1 and type 2 diabetes will result in improved well-managed glucose days, fewer episodes of severe hyper- and hypoglycemia, and improved patient satisfaction. We propose using existing subcutaneous CGM technology to monitor rapid, real-time glucose values in patients admitted to a Scripps hospital to determine the effectiveness of maintaining normoglycemia and reducing rates of hyper- and hypoglycemia and to evaluate patient and provider satisfaction with using this device in a hospital environment. All patients included in the study will be followed by an advanced practice diabetes nurse for glucose management during their hospitalization. All patients included in the study will receive a CGM. Patients with type 2 diabetes will be randomized to control (blinded CGM glucose values to APN,

care team and researchers) or intervention (CGM blood glucose values will be used to aid with glucose management during the hospitalization). In addition, a research only supplemental order set will be implemented for all study participants. The order set focuses on any glucose point of care test that is between 70-79 mg/dL at any time or \geq 201 mg/dl at night, between 9pm and 4am (21:00-04:00). The goal is to prevent hypoglycemia and hyperglycemia for all study patients. The advanced practice diabetes nurse will work with the physician in charge of the patient's care as well as the patient's care team. Historical baseline data for type 1 diabetes patients will be used as comparison for Aim 1 and Aim 4 below. Historical baseline data is defined as patients with type 1 diabetes admitted to a Scripps hospital within 24 months before first patient enrolled.

Aim 1 (observational): To compare the percentage of patient-days with average glucose in the target range (70-250 mg/dL) among patients with type 1 diabetes receiving CGM versus historical baseline data.

Aim 2: To compare the percentage of readings in the target range (70-250 mg/dL) among patients with type 2 diabetes randomized to control versus intervention.

Aim 3: To examine the acceptability and feasibility of using CGM in the hospital environment from patient (type 1 and type 2 diabetes) and provider perspectives.

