If the patient is to have a surgical procedure and the patient has been consented, then solely the sensor can be placed. The initial accuracy of CGM data is based on the length of time the sensor is in place and the CGM data has been shown to increase in accuracy with continued sensor wear. After the surgical procedure, the transmitter will be connected for communication of data to the receiver.

Sensor and transmitter will be removed before any CT, MRI or surgery. After procedure is complete, a new sensor can be placed if patient agrees.

Glucose Management

An Inpatient Glycemic Management Advanced Practice Registered Nurse Standardized Procedure (APN-S) will be followed (Appendix B: supplemental order set for subcutaneous insulin or PFO). The standardized procedure uses specific guidelines for the management of patients with diabetes within the hospital setting. The target goal for in-hospital blood glucose values are pre-prandial BG of 100-140 mg/dL and random BG less than 180 mg/dL.

Per PFO, if the initial POC testing value after alarm is 70-79 mg/dL then the patient will receive 15 gm glucose gel with follow up POC testing within 15 minutes. If the initial POC testing value after alarm is \geq 201 mg/dL anytime between 9pm (21:00) and 4am (04:00), and the patient has not received any insulin over the past three (3) hours, then patient will receive supplemental insulin dose, which is based on patient's current order of correction insulin. Communication will be ongoing between the advanced practice diabetes team, physician in charge of the patient's care as well as the patient's care team.

For Type 1 patients or Type 2 patients randomized in Intervention group, , CGM data will be used by APN to evaluate BG control of the patient every 24 hrs and/or earlier based on alarm CGM settings and rates of change arrows. The CGM device will be set to alarm if rate of change is trending towards hypoglycemia with a value of ≤ 90 mg/dL (arrow being shown will be , which means that if BG continues falling at this rate, BG could decrease up to 30 mg/dL in 15 minutes) or trending towards severe hyperglycemia with a value of ≥ 250 mg/dL (arrow being shown will be , which means that if BG continues rising at this rate, BG could increase up to 30 mg/dL in

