15 minutes). Trend arrows (rising, rapidly rising and falling and rapidly falling), will be taken into consideration looking at the whole patient picture, including nutritional intake and timing of meals/medications. When CGM alarms, "Followers" (which may include research staff and/or tele tech staff) will alert nursing staff assigned to the patient to conduct POC testing and treat patient accordingly per Research (PFO) or Hospital protocol (whichever applies).

For Type 2 patients randomized to the Control group, blood glucose values from CGM are not visible by APN or tele tech staff. PFO will still apply during any time patient gets a POC from bedside RN per standard hospital procedures.

Sensor Removal:

The sensor will be removed before hospital discharge, at day 10 post insertion, if the sensor fails for any reason or if the patient is to undergo a CT or MRI procedure. The sensor may also be removed at the discretion of the Principal Investigator. If the patient is to continue hospitalization, then a new sensor will be inserted. Once a sensor is removed, the insertion site will be examined for any inflammation/bleeding.

Follow-up:

A follow-up questionnaire will take place within 7 days from discharge (including discharge date) to assess any adverse events and to obtain patient satisfaction data regarding his/her hospital stay and use of the CGM device.

Provider satisfaction data will also be gathered (via focus group or questionnaire) after study patients have been discharged.

Measurements and Analysis

Clinical measures: Clinical measures that will be collected will include HbA1c on admission and at any time post admission while the patient is hospitalized, point of care glucose values conducted with the hospital based glucose meters (a minimum of four times a day) and CGM downloaded data. The reason for admission and patient medical history will be collected from the patient records.

Any change in insulin dosing per APN and/or physician will be collected.

Medications: All diabetes medication, steroids and acetaminophen use will be recorded.

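### The protocol and the order set it cites disagree on which earlier insulin withholds the night supplemental dose

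*Combined protocol and SAP*

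**What the plan says.** The night rule appears in three forms.

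- **Appendix B (the supplemental order set, or PFO).** The dose is given if "fingerstick blood glucose is greater than or equal to 200 mg/dL and no correction dose given in last three hours". Only an earlier correction dose withholds it. The form also tells staff: "Implement the below orders in addition to currently active insulin order set".
- **Protocol, Glucose Management.** This section names Appendix B as the PFO and presents its rule as coming from it. The condition is a high reading between 21:00 and 04:00 "and the patient has not received any insulin over the past three (3) hours, then patient will receive supplemental insulin dose". Insulin of any kind withholds the dose.
- **Synopsis and Study Design, type 1 and type 2 paragraphs.** Supplemental insulin is given only if the reading falls in the same hours and "they have not received any additional insulin for the past three hours". The term additional insulin is not defined.

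The order set has wide reach. The Synopsis overview says: "In addition, a research only supplemental order set will be implemented for all study participants". For type 2 controls, Glucose Management says: "PFO will still apply during any time patient gets a POC from bedside RN per standard hospital procedures".

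On the high-glucose alarm for the type 2 intervention arm, the protocol (Synopsis, Study Design, Glucose Management) requires a rising trend and states no hours. Appendix C, Analyses of T2D Subgroup, reports that telemetry notified nursing of values above 250 mg/dL from 9 p.m. to 4 a.m., without a trend condition. It reports low-glucose notification round the clock.

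**The concern.** The look-back decides whether a patient receives a further insulin dose at night. Glucose Management claims to restate the order set but states a different condition. For a patient whose only recent insulin was not a correction dose, the protocol and the form to be carried out at the bedside give opposite instructions. Staff cannot comply with both, and whichever is followed, the other is breached.

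What is at stake is patient safety and a clear record of what was done. The order set applies to type 1 patients and to both type 2 arms, so the conflict is not in itself a source of bias between the randomised groups.

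**Working it through.** No sample size or power calculation bears on this point. The check is a comparison of texts, with a few counts.

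**1. Same order, different rule.** Glucose Management identifies Appendix B as the PFO, so the first two columns should agree.

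| Element | Appendix B | Glucose Management | Synopsis and Study Design |
|---|---|---|---|
| Insulin in the past 3 h that withholds the dose | a correction dose | any insulin | additional insulin (undefined) |
| Trigger (mg/dL) | ≥ 200; dose scale starts at 201 | ≥ 201 | ≥ 201 |
| Window | after HS, no clock time, to 04:00 | 21:00 to 04:00 | 21:00 to 04:00 |

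**2. Where the look-backs part.** There are three cases for the past three hours:

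- No insulin: both texts dose.
- A correction dose, with or without other insulin: both withhold.
- Only non-correction insulin: Appendix B doses and Glucose Management withholds.

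An illustration with assumed values: fingerstick 230 mg/dL at 23:00, scheduled insulin at 21:30, no correction dose since 20:00. Appendix B gives a dose and Glucose Management does not. Under the Synopsis and Study Design, the answer depends on whether the scheduled dose counts as additional insulin.

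**3. Can the third case occur?** Nothing excludes it. The form runs alongside the patient's active insulin orders, and Appendix C says the analysed type 2 patients were on the hospital subcutaneous insulin protocol. The documents give no times for mealtime or basal insulin, so its frequency cannot be derived.

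**4. Trigger and window.** The trigger mismatch affects only a reading of exactly 200 mg/dL, which sets off the order in Appendix B but has no row on its dose scale. The HS window has no clock time, so it cannot be shown to match or to differ from 21:00.

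**5. How many patients are on the order set.**

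- Planned: 404 type 2 + 100 type 1 = 504.
- Analysed type 2: 57 + 53 = 110.
- Analysed, upper limit: 110 + 47 type 1 = 157. Appendix C describes the type 1 monitoring data as standard of care, so it is not certain that those 47 were on the order set.

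These are patients to whom the order set applies, not patients known to have received conflicting instructions.

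**6. Dates.** The form carries the date 22 August 2018 and the protocol version 9 January 2020: 365 + 140 = 505 days, about 16.6 months. The documents do not say whether the two were aligned.

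**7. Alarm (minor).** From 21:00 to 04:00 is 7 h, so the descriptions may differ for up to 24 − 7 = 17 h a day, or 17/24 = 70.8%, in the 57 intervention patients. This is an upper bound, because Appendix C describes one notification route and the protocol also allows research staff to relay alarms.

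**The case against.** The strongest reply is that the bedside instruction is the signed form, which contains a single rule. Glucose Management only paraphrases it and tells staff to treat under the research order set or the hospital protocol, whichever applies. On this view a nurse never holds two competing orders. The wording about additional insulin can also be read as agreeing with the form, which leaves Glucose Management as the one outlier. The form requires coordination with the diabetes advanced practice nurse and allows modification, and several sections call insulin adjustment individualised. Finally, the analyses are reported as done, so a correction may come too late to matter.

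Part of this stands. The firm contradiction is Glucose Management against Appendix B; the third wording is ambiguous rather than clearly opposed. The trigger mismatch has almost no practical effect, and the earlier form date proves nothing by itself. The alarm text may describe the hours in which telemetry acted rather than the device setting, so it may show incomplete reporting rather than contradiction.

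The rest does not remove the conflict. A protocol that misstates its own order set leaves compliance undefined, and coordination between nurses does not say which text governs. The sentences on individualised adjustment are followed by the same night restriction.

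**Conclusion.** The concern holds, with high confidence. Glucose Management and Appendix B give opposite instructions for any patient whose only insulin in the past three hours was not a correction dose, and no other section resolves this. It must be fixed, because it governs an insulin dose at night in an order set meant for every participant. That rating rests on the look-back alone.

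The number of patients affected is unknown. No sample size or power figure changes, and no bias in the randomised contrast is claimed. The trigger, window and alarm mismatches are minor and can be settled in the same edit. The conclusion assumes only that mealtime or basal insulin can fall within three hours before a night reading, which the documents do not exclude.

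**What to change.** The sponsor must reconcile the Synopsis and Study Design paragraphs for both diabetes types, Glucose Management and Appendix B into one wording for the look-back, the trigger value and the time window. The Synopsis overview and Specific Aims state only the trigger and window, and should match. Which rule applies is for the clinical team to decide. If the term additional insulin is kept, it needs a definition. If enrolment continues, the order form must carry the same wording.

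In the same edit, the protocol's high-glucose alarm text and the account in Appendix C should be aligned. Appendix C should say whether the reported hours were the only real-time route for high values and whether a trend was required. It should also say whether the 47 analysed type 1 patients were on the order set.

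For the 110 type 2 patients already analysed, an amendment changes nothing. A statement of which look-back was applied to them would be useful reporting but is not part of the required correction.

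The cost is a few sentences and, if enrolment is open, a corrected form. No extra patients or procedures are needed.
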